## **2.7.6 Other safety data**

### **2.7.7 ECG**

Twelve-lead ECGs will be performed for all patients at Screening and will be presented. All ECG data will be listed by patient and visit/time, abnormalities will be flagged. Summary statistics for observed and change from Baseline will be provided by visit.

### **2.7.8 Pregnancy and assessments of infertility**

For pregnancy, serum/urine test will be performed. Summary for the tests will be presented at Baseline and Week 24.

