Visit Name	Screening Visit	V1	V2 ¹²	V3	V4	Exit/V5		UPV
Visit Number	1	110	120	130	140	1999		UPV
Days	-28 days	1 (+3 days)	7 (±1 day)	28 (±5 days)	84 (±5 days)	168 (±5 days)	30- Day Telephone (±7 days)	
Obtain informed consent	Х							
MS History	Х							
Demography	Х							
Inclusion/Exclusion criteria	Х	Х						
Relevant Medical History	Х							
Physical Exam	S	S		S	S	S		S
Neurological Exam ⁸	X	X			X	X		X
Height	X					X		

Page 57 Protocol No. CBAF312AUS02

Period	Scree	ening				End of Treatment/St udy	Follow-up	Unplanned
Visit	Screening	Baseline ¹	Titration Treatment Period			End of Treatment/St udy	Safety	Unscheduled Visit
Visit Name	Screening Visit	V1	V2 ¹²	V2 ¹² V3 V4		Exit/V5		UPV
Visit Number	1	110	120	130	140	1999		UPV
Days	-28 days	1 (+3 days)	7 (±1 day)	28 (±5 days)	84 (±5 days)	168 (±5 days)	30- Day Telephone (±7 days)	
Weight	X	X			X	X		
Body Temperature	X	X		Χ	X	X		X
Respiration Rate	X	X		X	X	X		X
Blood Pressure	X	X		Χ	X	X		X
Heart Rate	X	X ²		Χ	X	X		X
Heart Rate 6 hours post Day 1 dose ²		Х						
Optical Coherence Tomography (OCT) ⁶		X _e			Х			
CYP2C9 Haplotype	Х							
Blood Chemistry/ Hematology	Х	Х		Х	Х	Х		Х
Coagulation and Thyroid	Х	Х		Х	Х	Х		Х
Hepatitis markers	Х							
CD19+ B-cell titer ¹⁰	X							

Period	Scree	ening			End of Treatment/St udy	Follow-up	Unplanned	
Visit	Screening	Baseline ¹	·		End of Treatment/St udy	Safety	Unscheduled Visit	
Visit Name	Screening Visit	V1	V2 ¹²	V3	V4	Exit/V5		UPV
Visit Number	1	110	120	130	140	1999		UPV
Days	-28 days	1 (+3 days)	7 (±1 day)	28 (±5 days)	84 (±5 days)	168 (±5 days)	30- Day Telephone (±7 days)	
VZV IgG Testing	X							
ECG (12 Lead)	X	X ⁷						
Pregnancy Test serum	S	S				S		
Pregnancy Test Urine				S	S			
AE/ SAE Assessment	Х	X		Х	Χ	X	Χ	X
Prior/Concomitant Medications	Х	Х		Х	Х	Х	X ⁵	Х
EDSS	Х							
TSQM-9		X		X	Χ	X		
C-SSRS		X				X		
Optional Trial Feedback Questionnaire ⁴		S			S	O		
Dispensation of medication ¹¹		S		S	S			

Period	Screening				Treatment		End of Treatment/St udy	Follow-up	Unplanned
Visit	Screening	Baseline ¹				End of Treatment/St udy	Safety	Unscheduled Visit	
Visit Name	Screening Visit	V1	V2 ¹²	V3	V4	Exit/V5		UPV	
Visit Number	1	110	120	130	140	1999		UPV	
Days	-28 days	1 (+3 days)	7 (±1 day)	28 (±5 days)	84 (±5 days)	168 (±5 days)	30- Day Telephone (±7 days)		
Drug accountability		S		S	S	S			
Dosage Administration Record		Х		Х	Х	X			
Washout ³		S							
IRT Call	S	S		S	S	S			

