- X = assessment to be recorded in the clinical database or received electronically from a vendor
- S = assessment to be recorded in the source documentation only
- 1. All baseline assessment are to be performed prior to siponimod dosing
- 2. Take another heart rate measure 6 hours post Day 1 dose (a Novartis-supplied portable heart rate monitor patch)
- 3. Patients currently taking or having taken teriflunomide in past 8 months will require a washout per label instructions prior to the baseline.
- 4. Patients may opt in or opt out of completing this questionnaire (optional).
- 5. Only SAEs and SAE related medications are to be collected.
- 6. OCT can be done 5 days prior to treatment or on Day 1 prior to treatment refer to Appendix 8.
- 7. ECG to be performed pre-dose on Day 1 (baseline) however, if the ECG assessment meets criteria in the protocol section 8.4.2., dosing cannot be initiated.
- 8. Neurological Exam refer to the protocol section 8.4 Table 8-2 for more details.

- 10. CD19+ titers only for patients previously exposed to ocrelizumab DMT.
- 11. Fingolimod patients will receive an additional telephone call from site staff at the end of BSL (Day 1) as part of additional safety measures.
- 12. There is no longer an ECG at Day 7 (visit 2). Therefore, visit 2 has been grayed-out and no longer applicable.

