8.2 Patient demographics/other baseline characteristics

Patient demographic and baseline characteristic data are to be collected on all patients include age, sex, race, and ethnicity. Relevant medical history/current medical condition data includes data until the start of study. Physical examination, vital signs, laboratory sampling, pregnancy testing, ECG, weight, and previous MS treatment, EDSS, will be recorded on eCRF. Where possible, diagnoses and not symptoms, will be recorded. MS medications will be recorded on eCRFs designed to facilitate separation from non-MS medications. The last RMS DMT administered right before converting to siponimod will be recorded. Likewise, detailed MS history and other relevant medical history will be recorded on eCRFs separately from relevant non MS medical. In order to collect accurate information about study drug exposure, records of study medication dispensed and returned, doses administered and visit dates should be maintained for each patient and transcribed into the Dosage Administration record eCRF. Compliance will be assessed by the investigator and/or study personnel at each visit. The study monitor will perform and document drug accountability during site visits and at the end of the study.

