8.4.4 Pregnancy and assessments of infertility

Serum pregnancy tests will be conducted for all women who are of child bearing potential at the screening, baseline, EOT/S visits of the treatment period.

Urinary pregnancy tests will be conducted for all women of childbearing potential at all other scheduled clinic visits as indicated in the schedule of assessments.

Relevant participants can perform the urine pregnancy test at home and report the result to the site. It is important that participants are instructed to perform the urine pregnancy test first and only if the test result is negative proceed with the administration of the study treatment. A communication process should be established with the participant so that the Site is informed of the pregnancy test results.

Assessments of Fertility

Medical documentation of oophorectomy, hysterectomy, or tubal ligation must be retained as source documents. Subsequent hormone level assessment to confirm the woman is not of child bearing potential must also be available as source documentation in the following cases:

- 1. surgical bilateral oophorectomy without a hysterectomy
- 2. reported 12 months of natural (spontaneous) amenorrhea with an appropriate clinical profile.

In the absence of the above medical documentation, FSH testing is required of any female patient, regardless of reported reproductive/menopausal status at screening/baseline.

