9.1 Discontinuation

9.1.1 Discontinuation of study treatment

Study treatment can be interrupted or discontinued based on investigator's judgement and overall clinical assessment, including in the following cases:

- Adverse event or serious adverse event (e.g., Serious infections, Symptomatic bradyarrhythmia)
- Abnormal laboratory value(s) including liver function tests
- Use of prohibited medications.

All dose changes must be recorded on the Dosage Administration Record eCRF.

Patients may voluntarily withdraw from the study for any reason at any time. They may be considered withdrawn if they state an intention to withdraw, fail to return for visits or become lost to follow up for any other reason. If premature withdrawal occurs for any reason, the investigator must make every effort to determine the primary reason for a patient's premature withdrawal from the study and record this information on the corresponding patient's disposition eCRF page.

Study treatment should be discontinued under the following circumstances:

- Withdrawal of informed consent
- Pregnancy
- Protocol violation that results in a significant risk to the patient's safety
- Non-compliance with study treatment
- Lost to follow up
- Emergence of certain adverse events, such as malignancy (except successfully treated basal cell carcinoma), liver failure or, serious chronic infections (such as HIV).

Note 1: For a patient with a positive urine pregnancy test, study medication must be immediately discontinued and a serum pregnancy test conducted. If the serum test is negative, the patient may restart study medication; if siponimod treatment has been interrupted for 4 or more consecutive daily doses, treatment must be re-initiated with the 5-day titration pack. If the serum test is positive, the patient can either be discontinued from the study or remain in the study continuing all scheduled visits, as above. Restart of study medication after the pregnancy (and lactation) will be considered on a case by- case basis, as above. Women who need another disease modifying treatment during pregnancy will be withdrawn from the study.

Page 71

The investigator must also contact the IRT to register any patient discontinuations from study treatment.

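### SAP 2.7.8 tabulates pregnancy tests only at Baseline and Week 24, leaves the placing of early positives undefined, and relies on data that Protocol Table 8-1 keeps out of the database

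*SAP*

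**What the plan says.** **Analysis.** SAP 2.7.8 refers to a serum/urine test and then says: "Summary for the tests will be presented at Baseline and Week 24". It plans no other pregnancy output. SAP section 3 declares no change from the protocol.

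**Schedule.** Protocol 8.4.4 sets two kinds of test. For serum: "Serum pregnancy tests will be conducted for all women who are of child bearing potential at the screening, baseline, EOT/S visits". For urine: "Urinary pregnancy tests will be conducted for all women of childbearing potential at all other scheduled clinic visits as indicated in the schedule of assessments". Table 8-1 puts the urine test at V3 (Day 28) and V4 (Day 84), and the serum test at Screening, V1 and V5.

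**After a positive result.** Protocol 9.1.1 says: "For a patient with a positive urine pregnancy test, study medication must be immediately discontinued". A serum test follows. If it is positive, the woman may leave the study or stay for all scheduled visits. Protocol section 8 asks for the end-of-treatment/study (EOT/S) visit when study drug is stopped early, and that visit includes a serum test.

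**Recording.** Both pregnancy rows of Table 8-1 are marked S. Its key reads: "S = assessment to be recorded in the source documentation only". Protocol 8.2 says otherwise: "pregnancy testing, ECG, weight, and previous MS treatment, EDSS, will be recorded on eCRF".

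**Windows.** SAP Table 1 gives Visit 5/EOS the window Day 127-183. SAP 2.1.1.4 combines windows for parameters not collected at every visit. SAP 2.1.1.5 keeps the worst record of a qualitative variable within a post-baseline window.

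**The concern.** A positive pregnancy test stops treatment, so a summary at one fixed late visit suits it poorly: the women of interest are those most likely to have left the visit schedule before then. The two on-study urine tests, which would usually give the first signal, have no place in the SAP 2.7.8 table. Whether the serum test that follows has a place depends on a windowing choice that the SAP does not make, so two programmers working from the same SAP could produce different tables from the same data.

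The second problem is more basic. If Table 8-1 governs, the results never reach the clinical database and the table cannot be produced at all, including its Baseline column.

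What is at stake is the description of on-treatment pregnancies in a trial whose protocol (4.5 and section 7) cites unknown risk to the fetus as the reason for its contraception requirements.

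**Working it through.** The plan gives no figure to reproduce here. The check maps scheduled tests to SAP windows.

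**Step 1: locate Week 24.** 24 × 7 = Day 168, which is Visit 5/EOS. The scheduled post-baseline tests are Day 28 (urine), Day 84 (urine) and Day 168 (serum). SAP 2.7.8 summarises one of the three.

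**Step 2: apply the window-combining rule.** The SAP Table 1 windows are Visit 2 Day 5-18, Visit 3 Day 19-56, Visit 4 Day 57-126 and Visit 5 Day 127-183. No pregnancy test is scheduled at Visit 2, so its window joins the next one used. Two readings are open:

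| Test result | Serum and urine pooled (V3, V4, V5): windows Day 5-56, 57-126, 127-183 | Serum alone (V5 only): window Day 5-183 |
|---|---|---|
| Urine positive, Day 28 | V3 window, not in Week 24 | not a serum result |
| Urine positive, Day 84 | V4 window, not in Week 24 | not a serum result |
| Confirmatory or exit serum, up to Day 126 | V3 or V4 window, not in Week 24 | in Week 24; worst-record rule keeps the positive |
| Exit serum, Day 127-183 | in Week 24 | in Week 24 |
| Woman stays and is still positive at Day 168 | in Week 24 | in Week 24 |

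Urine windowed alone has only Day 5-56 and Day 57-126, so no scheduled urine result reaches Week 24 under either reading. The readings differ only for serum results from Day 5 to Day 126. The SAP's wording treats serum and urine as one item, which leans towards pooling. Its pair of time points matches the on-study serum schedule, which leans towards serum alone. The text does not decide between them.

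**Step 3: check the data source.** With Table 8-1 (source only), there is no database input at Baseline, Day 28, Day 84 or Day 168. With Protocol 8.2 (eCRF), the input exists. However, 8.2 is headed as demographics and baseline characteristics, so its reach to post-baseline tests is uncertain.

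**Step 4: compare with other SAP sections.** For vital signs, SAP 2.7.9.1.2 adds a section for abnormalities at any time during treatment, using scheduled, unscheduled and premature-discontinuation visits. For laboratory shifts, SAP 2.7.5 uses the worst on-treatment value. Pregnancy testing has no equivalent. Pregnancy is not on the list of adverse events of special interest in SAP 2.7.3.

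**The case against.** The strongest reply is that early cases need not be lost. A woman who stops early has a serum test at her EOT/S visit, and a positive urine test leads to a serum test anyway. With serum as its own parameter, both results land in Week 24 and the worst-record rule keeps the positive. A woman who remains in the study and is still pregnant is counted at Day 168. Other outputs may also show the case:

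- SAP 2.3.1 lists the primary reason for each premature discontinuation.
- SAP 2.7.5 lists all laboratory data, and Protocol Table 8-4 counts pregnancy tests among the laboratory assessments.
- Protocol 10.1.4 requires every pregnancy to be reported to the sponsor within 24 hours and followed to outcome.

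Much of this stands. A reader might infer that pregnancies which stop treatment early cannot appear in the table, or that its post-baseline column would be close to zero by design. The documents do not support either, because the serum-only reading captures these cases. Nor do they support taking 84/168 = 0.50 as the share of pregnancies missed. That is elapsed time under an assumed constant rate; the boundary that matters is Day 126, and it matters only under pooling.

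The reply does not supply the missing windowing choice or remove the conflict over recording. The laboratory listing helps only if the results are in the database, which is the point in dispute. Disposition reasons give neither test results nor a percentage among women of childbearing potential. The 24-hour reports go to the sponsor's safety group, and the SAP does not draw on them.

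**Conclusion.** The point holds as a gap in specification together with a contradiction over where the data are recorded.

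- **Certain:** SAP 2.7.8 does not summarise the Day 28 and Day 84 urine tests, two of the three scheduled post-baseline tests. The Table 8-1 marking and Protocol 8.2 disagree and must be reconciled.
- **Conditional on pooling serum and urine:** a positive result up to Day 126 falls outside the Week 24 summary unless the woman stays and tests positive again in the Day 127-183 window.
- **Conditional on Table 8-1 governing:** the planned table has no database input at any time point.

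The documents give no expected number of pregnancies, so the number of affected women cannot be stated; it may well be small. The consequence is limited to a descriptive safety table. No hypothesis is tested on it, the primary endpoint is untouched, and expedited reporting of pregnancies continues regardless. This is a low-severity point, worth making because the remedy is nearly free.

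**What to change.** 1. Replace the SAP 2.7.8 summary with the number and percentage of women of childbearing potential who have any positive pregnancy test after the first dose, whether scheduled, unscheduled, confirmatory or at exit, with the study day of the first positive. Show serum-confirmed cases separately, since Protocol 9.1.1 provides for a positive urine test followed by a negative serum test. This follows the any-time approach the SAP already uses for vital signs and removes the need for a windowing rule.
2. Add a listing of reported pregnancies.
3. Make Table 8-1 and Protocol 8.2 agree on where results are recorded. Alternatively, draw the count from the Protocol 10.1.4 reports, limited to female participants with a pregnancy detected after first dose, because that section counts from informed consent. A count from these reports covers pregnancies, not every positive urine test, and the table should say so.
4. If childbearing status is not in the database, use all women in the Safety Set as the denominator and label it so.

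The cost is SAP wording and at most one eCRF field, or no field if the pregnancy reports are used. No test, visit or treatment rule changes.

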### **2.7.9 Vital signs**

Vital signs measurements include pulse, systolic blood pressure, diastolic blood pressure, temperature, body weight and heart rate. The following summaries will be presented on the safety set.

#### **2.7.9.1.1 Summary of absolute values and change from Baseline**

Vital signs including the changes from Baseline will be summarized at the scheduled visits and time points.

Change in heart rate from Baseline to 6-hour after first treatment will be summarized as the secondary endpoint.

All vital signs data will be listed by patient and visit/time and if ranges are available, abnormalities will be flagged.

#### **2.7.9.1.2 Notable absolute values and change from Baseline**

The number and percentage of patients with newly occurring or worsening notable values, including notable change from Baseline, will be summarized by vital sign parameter and post-Baseline visit. An additional section will be included for abnormalities occurring at any time point over the treatment period, considering all post-Baseline data from scheduled, unscheduled and premature discontinuation visits. Notable absolute values and notable changes from Baseline for each vital sign parameter are defined in the Table 4 :

**Table 4 Criteria for notable vital sign abnormalities**

Vital Sign Variable	Notable Criteria
Pulse (beats/min)	>120 bpm Or < 50 bpm
Systolic BP (mmHg)	≥ 160 mmHg Or ≤ 90 mm Hg
Diastolic BP (mmHg)	≥ 100mmHg Or ≤ 50 mmHg
Temperature (°C)	>38.3 °C/ 101°F
Body weight (kg)	± 7% from Baseline weight

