Note: If the treating physician suspects false positive hepatitis serology results, such as an antibody pattern indicating acute hepatitis infection but no corresponding elevated liver enzymes and no signs or symptoms of liver disease, a HEV-RNA PCR will be performed and will be the deciding factor to determine whether the patient has hepatitis A, B, C, or E. If negative, the treating physician may document (in source data and in a eCRF comment) that the serology results are considered false positive and consider including the patient.

- 10. Negative for varicella-zoster virus IgG antibodies at Screening unless there is other evidence of immunity to VZV based on the CDC criteria (https://www.cdc.gov/chickenpox/hcp/immunity.html; see Appendix 1)
- 11. Have received any live or live-attenuated vaccines (including for varicella-zoster virus or measles) within 2 months of screening.
- 12. Have been treated with any of the medications listed below:

- Intravenous immunoglobulin within 2 months prior to screening
- Immunosuppressive/chemotherapeutic medications (e.g., azathioprine, methotrexate) within 6 months prior to screening
- Cyclophosphamide within 2 years prior to screening
- More than 24 months prior treatment exposure to natalizumab
- Rituximab, ofatumumab, ublituximab or cladribine within 2 years prior to randomization
- Alemtuzumab at any time
- Any mitoxantrone during previous 2 years prior to randomization or evidence of cardiotoxicity following mitoxantrone or a cumulative life-time dose of more than 60 mg/m2
- If patients treated with teriflunomide cannot or will not undergo the accelerated elimination process Appendix 6.
- Stem cell transplantation
- Lymphoid irradiation, bone marrow transplantation or other immunosuppressive treatments with effects potentially lasting over 6 months, at any time.
- 13. Patients with any medically unstable condition as determine by the investigator.
- 14. Any of the following conditions or treatments that may affect cardiovascular function within the last 6 months:
 - Heart rate < 55 bpm at screening
 - Cardiac conduction disorders such as incomplete left bundle branch block or second degree AV block Mobitz type I (Mobitz I) (either history or observed at screening)
 - Minor ECG findings at screening PR interval: >200 msec; QRS duration ≥120 msec; QTcF >430 msec (males); QTcF >450 msec (females)

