Vital signs will be assessed at every visit. This will include blood pressure and heart rate measurements. BP will be medium sized cuff and the noon-dominant arm in the sitting position after 5 minutes of rest. Every effort should be made to use the same arm for the patient for all vital signs assessments and where possible, the same person doing the assessment. Clinically notable vital signs are defined in Appendix 1.

8.4.1 **Laboratory evaluations**

Table 8-4 **Laboratory Assessments**

I able 0-4	Laboratory Assessments	
Test Category	Test Name	
Hematology	Red blood cells, total White blood cells, Differential White blood cells (Basophils, Eosinophils, Lymphocytes, Monocytes, Neutrophils, platelet count, hemoglobin, hematocrit, mean corpuscular volume, mean corpuscular hemoglobin, mean corpuscular hemoglobin concentration and red blood cell morphology	
Chemistry	Alkaline phosphatase, ALT, AST, Gamma-glutamyl-transferase (GGT), Bicarbonate, Calcium, Magnesium, Phosphorus, Chloride, Sodium, Potassium, Creatinine, Creatine kinase, Direct Bilirubin, Indirect Bilirubin, Total Bilirubin, Total Cholesterol, LDL, HDL, Total Protein, Triglycerides,	
	Glucose, amylase	
Coagulation	Prothrombin time (PT) , Partial thromboplastin time (PTT)	
Thyroid	T3 (free), T4 (free), TSH	
Hepatitis markers	HBV-DNA, HbsAg, HbsAb, HbcAb, HCV RNA-PCR (baseline)	
Additional tests	Serology: anti-hepatitis A virus IgM, hepatitis B surface antigen and anti-hepatitis B core antigen IgM, anti-hepatitis C virus IgG or IgM, anti-hepatitis E virus IgM (positive IgM and/or IgM: do HEV-RNA PCR; if negative, patient can be included), Anti-VZV IgG, CYP2C9 haplotype testing	

Test Category	Test Name
	CD19+ Titers
Pregnancy Test	Serum / Urine pregnancy test

Clinical Chemistry

Blood samples will be collected at the scheduled visits indicated in Table 8-1, and the parameters assessed will include: electrolytes (Na, K, Cl, bicarbonate, Ca, Mg, P), random glucose, albumin, alkaline phosphatase, creatinine, ALT, AST, GGT, amylase, total bilirubin, conjugated bilirubin, total cholesterol, CRP, triglycerides, HDL and LDL.

Hematology

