8.4.2 Electrocardiogram (ECG)

Twelve-lead ECGs will be performed for all patients at Screening, Baseline (Day 1; Pre-dose). Clinically significant abnormalities should be recorded on the Medical History/Adverse event eCRF page.

If the Day 1 (pre-dose) 12- lead ECG assessment meets any of the following criteria, then dosing cannot be initiated.

The criterion are:

- 1. Heart rate < 55 bpm
- 2. Cardiac conduction disorders such as incomplete left bundle branch block or second degree AV block Mobitz type I (Mobitz I) (either history or observed at screening)
- 3. Minor ECG findings: PR interval >200 msec; QRS duration ≥120 msec; QTcF >430 msec (males); QTcF >450 msec (females)
- 4. Any other condition which, in the opinion of the investigator, has a potential for AV conduction suppression
- 5. Patients diagnosed with right bundle branch block

If none are met, then the patient can continue with treatment.

Additionally, on baseline Visit 1 (Day 1), heart rate will be monitored and measured for 6 hours on a holter telemetry device post initial dose of siponimod. If post-dose HR remains < 45 bpm at the end of 6-hour post-dose monitoring period, additional monitoring may be required (see Appendix 7).

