12.5 Analysis of secondary endpoints

12.5.1 Safety endpoints

Safety summaries (tables, figures) include only data from the on-treatment period with the exception of baseline data which will also be summarized where appropriate (e.g. change from baseline summaries). In addition, a separate listing for death including on treatment and post treatment deaths will be provided. In particular, summary tables for adverse events (AEs) will summarize only on-treatment events, with a start date during the on-treatment period (treatment-emergent AEs).

The on-treatment period lasts from the date of first administration of study treatment to 30 days after the date of the last actual administration of any study treatment.

Adverse events

All information obtained on adverse events will be displayed by patient.

The number (and percentage) of patients with treatment emergent adverse events (events started after the first dose of study medication or events present prior to start of open-label treatment but increased in severity based on preferred term) will be summarized in the following ways:

- By primary system organ class and preferred term
- By primary system organ class, preferred term and maximum severity
- By Standardized MedDRA Query (SMQ) and preferred term

Separate summaries will be provided for adverse events and other significant adverse events leading to discontinuation.

The number (and proportion) of patients with adverse events of special interest/related to identified and potential risks will be summarized.

A patient with multiple adverse events within a category (overall, primary system organ class, or preferred term) is only counted once towards the total of that category.

In addition, occurrence of hospitalization will be summarized using frequencies and percentages.

Vital signs

All vital signs data will be listed by patient, and visit/time and if ranges are available, abnormalities will be flagged. Summary statistics will be provided by visit/time.

In addition, change in heart rate from Baseline to 6-hour after first treatment will be summarized.

12-lead ECG

All ECG data will be listed by patient and visit, abnormalities will be flagged. Summary statistics will be provided by visit.

In addition, change in heart rate (and other vitals) from Baseline to 6-hours after first treatment, may be summarized. Please see protocol Section 8.4.2

Clinical laboratory evaluations

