## 1 Introduction

This document contains details of the statistical methods which will be used in the phase IIIb clinical trial CBAF312AUS02. The statistical analysis described in this SAP is based on the study protocol no. BAF312AUS02 Amendment Version 05 and will be presented in the Clinical Study Report (CSR). This document will also describe planned analysis for an interim analysis.

The purpose of this study is to assess early phase safety and tolerability of converting patients from approved oral, injectable or infusion RMS DMTs to siponimod. The results of this phase IIIb clinical trial CBAF312AUS02 will guide clinically relevant decisions related to the transition from frequently used RMS DMTs to siponimod and provide clinically relevant data on safety and tolerability for healthcare providers who are considering converting patients from currently approved RMS DMT to siponimod.

[figure not shown]

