## **3 Change to protocol specified analyses**

Not Applicable.

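### SAP Table 4 counts a low pulse as notable below 50 bpm, while protocol Appendix 1 sets the limit at 55 bpm, and no reason for the difference is recorded

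*SAP*

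**What the plan says.** Protocol section 8.4, under vital signs, states: "Clinically notable vital signs are defined in Appendix 1". Appendix 1 (section 16.1) lists pulse as notable above 120 bpm or below 55 bpm.

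SAP 2.7.9.1.2 plans the number and percentage of patients with new or worsened notable values, by parameter and post-Baseline visit. It adds an any-time section "considering all post-Baseline data from scheduled, unscheduled and premature discontinuation visits". Table 4 holds the criteria, and its pulse row reads ">120 bpm Or < 50 bpm".

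The SAP introduction says that the analysis "is based on the study protocol no. BAF312AUS02 Amendment Version 05", which is the protocol version under review. SAP section 3, "Change to protocol specified analyses", is marked as not applicable.

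Protocol section 12.5.1 asks for vital-sign listings in which "if ranges are available, abnormalities will be flagged", plus summary statistics by visit. It does not ask for a table of notable-value counts.

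**The concern.** One term, notable pulse, has two definitions in the trial's governing documents, and nothing says that the difference is intended. A reader with the protocol in hand who takes the SAP table to use the protocol's definition would see too few patients.

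The cell matters more than most because of the drug. Protocol section 4.5 names bradyarrhythmia after the first dose as a siponimod risk, and cardiac safety at treatment initiation is a secondary objective.

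The protocol's own entry rules make the gap more than cosmetic. Exclusion criterion 14 includes "Heart rate < 55 bpm at screening". Section 8.4.2 lists a heart rate below 55 bpm among its Day 1 criteria and says: "If the Day 1 (pre-dose) 12- lead ECG assessment meets any of the following criteria, then dosing cannot be initiated". A treated patient should therefore start at 55 bpm or above. A later value from 50 to below 55 bpm would then normally be newly notable under Appendix 1, which is the kind of case that SAP 2.7.9.1.2 sets out to count.

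**Working it through.** **Row-by-row comparison**

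| Variable | Protocol Appendix 1 | SAP Table 4 |
|---|---|---|
| Pulse, high | > 120 bpm | > 120 bpm |
| Pulse, low | **< 55 bpm** | **< 50 bpm** |
| Systolic BP | ≥ 160 or ≤ 90 mmHg | ≥ 160 or ≤ 90 mmHg |
| Diastolic BP | ≥ 100 or ≤ 50 mmHg | ≥ 100 or ≤ 50 mmHg |
| Temperature | > 38.3 °C / 101 °F | > 38.3 °C / 101 °F |
| Body weight | ± 7% from baseline | ± 7% from baseline |

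Only the low-pulse limit differs, by 5 bpm. The protocol's other low heart-rate limits are 55 bpm (5.2, 8.4.2, 10.2.3) and 45 bpm post-dose (8.4.2, 10.2.3, Appendix 7). A heart-rate limit of 50 bpm appears nowhere in it.

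**What the SAP rule leaves out**

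- By visit: a reading from 50 to below 55 bpm is not counted at that visit.
- Any time: a patient whose lowest post-Baseline reading lies in that interval is not counted at all.

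**Illustration of size**

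The documents give no mean, SD or within-patient correlation for heart rate, so the true number cannot be computed.

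Inputs from the documents:
- the 55 bpm rules at screening and at Day 1 pre-dose
- n = 300 to 400
- a maximum fall in mean heart rate of 5.3 bpm on Day 1, at 4 hours, in the phase III trial described in protocol section 1.1

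Assumed inputs:
- multivariate normal readings at screening, Day 1 pre-dose, 6 hours and Visits 3, 4 and 5, with equal correlation between all of them
- mean 68, 70, 72, 74 or 76 bpm; SD 8, 10 or 12; correlation 0.5 or 0.7

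Simulated patients are kept only if the screening and Day 1 pre-dose values are both at least 55 bpm. The gap is P(below 55) − P(below 50) among those kept, and the number of patients is n × gap.

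| Reading | Below 55 | Below 50 | Gap | Of 300 | Of 400 |
|---|---|---|---|---|---|
| One later visit, no shift in mean | 0.29%–8.09% | 0.02%–3.13% | 0.27%–4.95% | 1–15 | 1–20 |
| Day 1 post-dose, mean 5.3 bpm lower | 2.09%–18.02% | 0.33%–8.50% | 1.77%–9.92% | 5–30 | 7–40 |

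For the any-time section, the lowest of the 6-hour, Visit 3, Visit 4 and Visit 5 readings is used:

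- No shift at 6 hours: 0.97%–23.5% are below 55 bpm and the gap is 0.88%–13.2%.
- A 5.3 bpm fall at 6 hours: 2.55%–29.9% are below 55 bpm and the gap is 2.17%–15.4%.
- Combined range of the gap: 0.88%–15.4%. This is 300 × 0.0088 = 2.6 to 300 × 0.154 = 46.2 patients, or 400 × 0.0088 = 3.5 to 400 × 0.154 = 61.6.

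One worked case has mean 72, SD 10 and correlation 0.7. At a single later visit, 2.20% are below 55 bpm and 0.43% below 50 bpm, or about 9 against 2 of 400. With the 5.3 bpm fall the figures are 8.27% and 2.40%, or about 33 against 10 of 400.

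Across this grid, 51% to 92% of patients below 55 bpm lie at or above 50 bpm, so more than half of those notable under Appendix 1 would not be counted. A repeat simulation gave the same figures within simulation error.

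**The case against.** The mismatch itself is not in dispute. The case for treating it as minor has five parts.

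- **No planned analysis was changed.** Protocol section 12.5.1 does not request this count. The SAP added a table and set its own criterion, so section 3 is not false. This stands. The conflict is with the definition in section 8.4 and Appendix 1.
- **The limit is printed.** Anyone who reads Table 4 sees 50 bpm. That is true, but a row-for-row copy of Appendix 1 with one cell changed and no comment does not show whether 50 bpm was chosen or mistyped.
- **Low heart rate is covered elsewhere.** Bradyarrhythmia/bradycardia is an adverse event of special interest. The 6-hour change is a secondary endpoint reported with its minimum and quartiles. Listings and by-visit summaries keep every value. A limit of 50 bpm also captures everything below the protocol's post-dose limit of 45 bpm. All of this stands and limits the consequence to one table.
- **The pulse row may not cover the 6-hour heart rate.** SAP 2.7.9 lists pulse and heart rate separately, and the protocol schedules heart rate. The SAP's definition of post-Baseline values and its any-time section imply that the 6-hour reading counts, but the SAP does not say so. The Day 1 and any-time figures depend on that reading.
- **The percentages reflect the chosen grid.** With means of 72–80, SDs of 6–10 and correlations of 0.6–0.8, the any-time gap runs from near zero to about 9%. With means of 65–75, SDs of 8–12 and correlations of 0.5–0.7, it runs from about 1.2% to 20%. The 5.3 bpm figure comes from another trial with titrated initiation, whereas current fingolimod converters start here without titration. This stands: the figures show that the gap need not be trivial, and they do not estimate it.

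**Conclusion.** The concern holds. The SAP uses a low-pulse limit for notable values that differs from the one in the protocol it is based on, and the difference is recorded and explained nowhere. Followed as written, the SAP omits from its notable-value counts readings from 50 to below 55 bpm, which the protocol's definition includes.

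The true number of patients is unknown, and in absolute terms it may be small. The illustrative figures assume normality, equal correlation and the stated means and SDs. Those for Day 1 and any time also assume that the 6-hour reading belongs in the pulse row.

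The consequence is limited to this one descriptive table. The primary endpoint, the heart-rate change endpoint, the tables of adverse events of special interest, the listings and the by-visit summaries do not change. The correction should be made because the inconsistency is certain, it sits in the vital sign closest to the drug's known risk, and it is cheap to remove. No view is taken here on which limit is clinically right.

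**What to change.** - Reconcile the pulse row of SAP Table 4 with protocol Appendix 1, or show counts below 55 bpm and below 50 bpm side by side. A row for the protocol 10.2.3 post-dose limit of 45 bpm is optional.
- If a difference from Appendix 1 is intended, record it with its reason in SAP section 3.
- As a clarification, add a sentence to SAP 2.7.9 saying that the pulse row covers heart rate and that the 6-hour Day 1 reading counts as post-Baseline.

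The cost is one cell or one added row, one sentence and one line in section 3, all using data already collected. The downside of counting at 55 bpm is more flagged patients in one descriptive table, many of them with values that may have no clinical consequence. Showing both limits lets the reader tell the two groups apart.
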